## **Subject criteria**

### **Inclusion criteria**

- Diagnosis of type 1 diabetes mellitus for at least 1 year
- Male or female participants 18 years of age or older
- Using multiple daily injections
- HbA1c <10% at screening
- Current use of a continuous glucose monitoring system with at least two episodes of overnight hypoglycemia (defined as sensed glucose <70 mg/dL for at least 10 minutes between the hours of 10 PM and 6 AM) within 30 days prior to screening
- Individuals with history of severe hypoglycemia requiring third party assistance must have a companion in the same dwelling as the study participant who will be linked to the participant's Dexcom app during the control arm of the study, and who is trained in the administration of glucagon.
- Willingness to follow all study procedures
- Willingness to sign informed consent and HIPAA documents

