### **Control arm (4 weeks)**

There will be a visit at the start of the control arm that will be held virtually using WebEx. This visit can be held in clinic. The purpose of this visit is to have the participants learn how to use study devices and the Dexcom app. Using the Webex platform, study staff can connect virtually

with participants for training on the devices and study procedures while they are at home. Participants will be trained in how to use the Dexcom G6 CGM system for those not already using the Dexcom G6 system including insertion, sensor change, and calibration. For participants who are current users of Dexcom G6 CGM system, the insertion, change, and calibration of the Dexcom G6 CGM device will not be discussed during this meeting. Participants will be trained in how to pair the Dexcom G6 transmitter to the Dexcom app on a provided study smart phone, to start and stop a new sensor session, and how to enter calibrations. The CGM alerts will be set at 70 mg/dL and 250 mg/dL. For participants with history of severe hypoglycemia requiring third party assistance, low glucose alerts will be conservatively set to 85 mg/dL. Participants can modify these settings. Participants will be instructed to manage their glucose as they normally do. For those participants with history of severe hypoglycemia requiring third party assistance, a participant's companion (who lives in the same house and is trained in the administration of glucagon as per study inclusion criteria) will be linked to the participant's Dexcom app. The Apple Watch will be paired with the Apple iPhone by the study staff before giving them to participants. Participants will be trained in how to use the Apple Watch, which will be used during the study to collect sleep data. This visit will take approximately 0.5 - 1.5 hours, depending on the subject's experience.

At the beginning of the control period, participants will record their weight using a scale provided by the study staff. During the 4-week control period, participants will wear Dexcom G6 CGM and the study Apple Watch. The Apple Watch will be used to track sleep metrics; therefore, participants are asked to wear the smart watch overnight and charge it during the day.

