### **DailyDose + *smart snack* intervention arm (4 weeks)**

There will be a visit at the start of the intervention arm that will be held at OHSU's Biomedical Engineering Artificial Intelligence for Medical Systems (AIMS) Laboratory, the Harold Schnitzer Diabetes Health Center, or virtually using WebEx. A urine pregnancy test might be required for individuals of childbearing potential if the last pregnancy test was more than 7 days prior. This test must be negative before further participation is allowed. During this session, participants will go through the onboarding process with the DailyDose app. This process will occur with the study staff and involve:

- Training on using the Dexcom G6 CGM within the DailyDose app
- Setting up low and high blood glucose CGM-based alerts

- Setting up bedtime for running nocturnal low glucose prediction and receiving bedtime snack recommendation when applicable
- Review *smart snack* options that will be recommended by DailyDose and provided to participants during the intervention period (study protocol, Table 1) as well as present accessible snack alternatives (e.g., those already documented in the study protocol Table 2), in case participants has any allergies or food aversion related to DailyDose *smart snack* options. The study staff will also provide a card with bedtime snack options and replacements so that participants can easily find adequate alternatives to the snacks recommended by DailyDose (study protocol, Appendix F).
- Training on usage of the DailyDose app including how to setup alerts, predict likelihood of nocturnal low glucose, accept/decline *smart snack* recommendations, and use of the insights tab / settings / logbook features
- Training on usage of the Apple Watch

DailyDose has glucose alerts for safety. The Dexcom G6 CGM alerts in DailyDose will be set at 70 mg/dL and 250 mg/dL with user able to adjust. For participants with history of severe hypoglycemia requiring third party assistance, low glucose alerts will be conservatively set to 85 mg/dL. There is a very low glucose alert (glucose <55 mg/dL) that cannot be adjusted.

This visit will take approximately 2-3 hours, depending on the subject's experience.

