#### **Washout period (1 - 4 weeks)**

There will be a one- to four week washout period between the control and intervention arms (or between intervention and control arms depending on randomization sequence). The use of the DailyDose app will be discontinued during this period for those participants who were randomized to start using DailyDose. Participants will use their own sensors during the washout period and will manage their glucose as they normally do. Participants are not required to weigh themselves, complete questionnaires, or wear the Apple Watch during this week. No visits are scheduled during the washout period.

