due to technical problems, the participant may be asked if they can complete additional time in study with the goal to collect at least 2 weeks worth of data in at least one of the arms of the study, such that the participant can be included in the statistical analysis. Additional compensation will be provided for additional time in study. Problems that would qualify for extending the study time are 1) insufficient study supplies requiring the participant to go off of DailyDose + smart snack intervention or to discontinue the control arm for a period of time (such as running out of CGM supplies or bedtime snacks), 2) issues with the smartphone such that DailyDose cannot be used/accessed (such as a due to a damaged phone or problems with the internet connection that prevent data from being uploaded to the remote monitoring system), 3) issues with the CGM system or the capture of the CGM data during the control period or during the intervention period such that DailyDose cannot generate bedtime recommendations due to insufficient CGM data, or 4) scheduling issues such that the participant is unable to complete the control or the DailyDose + smart snack intervention period continuosly. Participants can complete up to 4 additional weeks to make up time the study was paused for technical reasons. Repeating the study time will be optional. The study team will track when participants extend their study time and the reason and this will be included in the annual report to the FDA.

Table 3: Schedule of Events

 DailyDose abbreviated Dd

 Randomization order abbreviations Control first (CG) Intervention first (IG)

 (CG) only

(IG) only

Collect demographic and other baseline characteristics	X											
UPT if applicable and not done in last 7 days (Point of care)	X	X						X				
Collect blood sample for HbA1c, CBC, CMP, TSH testing	X											
Collect information about medical history	X											
Collect information about concomitant medications	X	X	X	X	X	X	X	X	X	X	X	
Download participant's glucose sensor	X											
Complete 3 surveys	X					X 					X 	
Randomization		X										
Collect data on Adverse Events		X	X	X	X	X	X	X	X	X	X	
Train participants on the study procedures to do at home		X					X					
Train participants on use of Dexcom G6 CGM system with G6 and Clarity apps		X 					X 					
Train participants on use of Apple Watch		X										

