## Stopping rule criteria

The study will be stopped if any of the following occur after the start of the study:

- The participant requests that the treatment be stopped
- Participant pregnancy
- One episode of diabetic ketoacidosis as defined as symptoms such as polyuria, polydipsia, nausea, or vomiting, serum ketones  $>1.5$  mmol/L or moderate/large urine ketones, either arterial blood pH  $<7.3$  or venous pH  $<7.24$  or serum bicarbonate  $<15$ , and treatment provided in a health care facility.
- One episode of severe hypoglycemia defined as a hypoglycemic event resulting in altered consciousness requiring another person to actively administer carbohydrate, glucagon, or other resuscitative actions.

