## Data Collection

We will be collecting de-identified physiologic data from people with T1D. The following data will be collected from participants in this study:

- Glucose sensor data (Dexcom G6 system)
- Self-report *bedtime snack* and exercise data logged by the participant on DailyDose
- Self-report weight logged by participant
- Sleep data from Apple Watch
- Responses to surveys

To collect the data, each participant in the study will be given an Apple iPhone and an Apple Watch. The iPhone will have the Dexcom G6 app and the DailyDose app installed. These apps will collect CGM data and log related to physical activity, bedtime snacks, and overnight low glucose predictions. The data from the Apple Watch will be exported from Apple Health or Apple iTunes as .cda or .xml files.

The DailyDose app will serve as the “data aggregator” on the phone and will perform the following functions:

- Collect self-report bedtime snacks and exercise data from the participants
- Aggregate all the data collected from the glucose sensor and self-logged snacks and exercise data
- to be stored as de-identified data within the iCloud storage area of the phone

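### For participants with prior severe hypoglycemia, the companion's Dexcom link is required in the control arm only, and the intervention arm states no way of notifying the companion

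*Combined protocol and SAP*

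**What the plan says.** The Inclusion criteria admit people with earlier severe hypoglycemia on condition that they have a live-in companion. Living in the same home and glucagon training carry no arm limit. The data link does: the companion is to be "linked to the participant's Dexcom app during the control arm of the study".

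The section Control arm (4 weeks) carries this out. At the control start visit the companion, who is "trained in the administration of glucagon as per study inclusion criteria) will be linked to the participant's Dexcom app", is connected. These participants' low alert starts at 85 mg/dL, and participants may change it.

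The section DailyDose + smart snack intervention arm (4 weeks) repeats the alert setting for the same people: "low glucose alerts will be conservatively set to 85 mg/dL. There is a very low glucose alert (glucose <55 mg/dL) that cannot be adjusted". Its onboarding list includes "Training on using the Dexcom G6 CGM within the DailyDose app". It says nothing about a companion or a link.

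Under Data Collection, "The iPhone will have the Dexcom G6 app and the DailyDose app installed". The section on the GRM Cloud Server says that app data go to a server every five minutes and can be seen on a physician portal.

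**The concern.** The protocol itself decided that these participants need someone else who can see their glucose, and it gives no reason why that need should end when the study app is in use. A severe low is defined under Stopping rule criteria as one "requiring another person to actively administer carbohydrate, glucagon, or other resuscitative actions". Rescue therefore depends on another person knowing that help is needed. Risk and Benefits relies on the app's alerts to make severe lows unlikely, while the Background observes that sleeping people are less likely to wake to CGM alarms. A companion who is in the home but is not notified may not know to act.

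There is also a design point. A linked companion is a form of extra care. If it is given in one arm and not the other, the arms differ by something besides the snack intervention.

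**Working it through.** The plan states no figure for this point, so the check is a comparison of the text by arm, followed by a count of nights.

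| Safeguard for participants with prior severe hypoglycemia | Control arm | Intervention arm |
|---|---|---|
| Live-in companion trained in glucagon | Required (Inclusion criteria, no arm limit) | Required (same text) |
| Companion linked to the Dexcom app | Required (Inclusion criteria; Control arm section) | Not stated |
| Low alert at 85 mg/dL | Yes, adjustable | Yes; the section describes the DailyDose alerts as user-adjustable |
| Fixed alert below 55 mg/dL | Not stated | Yes |
| Physician portal fed by DailyDose | Not stated as a safeguard | Yes, but not described as watched overnight or as contacting the companion |

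**Is there another route to the companion in the intervention arm?** The 85 mg/dL and below-55 mg/dL alerts are described as alerts in the participant's app, and neither is said to reach anyone else. The portal shows data to physicians. I found no statement elsewhere in the protocol of a channel that notifies the companion in this arm.

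**Does the order of arms matter?** In the control-first sequence the link is set up in the first arm. No section says that it is then removed, so it may continue in practice. In the intervention-first sequence the text gives staff no instruction to set it up until the control arm begins. This follows from the Inclusion criteria and the Control arm section alone. Table 3 has a training row, "Train participants on use of Dexcom G6 CGM system with G6 and Clarity apps", with sequence footnotes, but the table is only partly legible in the text available and I do not rely on it.

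**Count of nights.** Endpoints gives 27 nights per condition.

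- Planned nights per participant: 27 + 27 = 54.
- Nights with a stated link: 27 (control). Share: 27 / 54 = 50%.
- Intervention nights with no stated link: 27.

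This counts nights on which the text is silent. It does not measure risk.

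**Planned frequency of lows.** The Power analysis assumes a nightly risk of 0.18 in control and 0.09 in the intervention period.

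- Control: 0.18 × 27 = 4.86 nights per participant.
- Intervention: 0.09 × 27 = 2.43 nights per participant.

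These are nights with glucose below 70 mg/dL among all participants. They are not severe events and are not specific to this subgroup. They show that lows are still expected on some intervention nights, and that the plan expects fewer of them than in control.

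**Effect on the primary endpoint.** A night counts once there are at least two readings below 70 mg/dL in the eight hours after bedtime. The protocol gives neither the companion's alert threshold nor the expected response.

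- If the companion is alerted only after two such readings, the night is already an event and the link changes nothing.
- If the alert comes earlier and the companion acts, some control-arm events could be avoided.

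Without the threshold, the response and the number of qualifying participants, neither size nor direction can be established.

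**The case against.** The strongest reply is that the arms have different safeguards, and that the intervention arm has not simply lost one. The control arm runs on the Dexcom app, so a link to that app belongs there naturally. The intervention arm uses the sensor through DailyDose, which has an alert that cannot be adjusted and which streams data to a server. The companion is still in the home. The inclusion criterion sets a requirement for one arm and does not forbid a link in the other. The subgroup may be empty, the companion may also be asleep, and the documents do not confirm that Dexcom sharing works alongside DailyDose.

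Most of this stands, and it limits the weight of the point. It does not answer it: none of the intervention-arm safeguards is said to reach the companion, and staff who follow the intervention start visit as written would have no instruction to connect one.

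Three stronger readings are tempting and are not supported.

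- **That the snack arm is more dangerous.** The Background says that DailyDose's insulin-dosing and exercise features are not used. The intervention adds an optional bedtime snack of about 15 to 30 g carbohydrate to usual management. The overnight glucose risk that Risk and Benefits attributes to the snack is hyperglycemia, and the planned risk of a low is half that of control (0.09 / 0.18 = 0.5).
- **That the asymmetry biases the trial against the intervention.** As shown above, the effect may be nil, and its direction cannot be fixed from the documents.
- **That the washout is part of the gap.** Under Washout period, "Participants will use their own sensors during the washout period and will manage their glucose as they normally do". That is usual care, and no study link is called for there.

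**Conclusion.** The point holds as a minor safety gap and a difference in co-intervention between the arms. The protocol requires the companion's link in the control arm only, and it states no channel that notifies the companion during the intervention arm. The extent is 27 of 54 planned nights per qualifying participant. The number of qualifying participants is not given and may be zero, and the benefit of a link cannot be sized. I therefore claim no change in event risk, relative risk or power.

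The conclusion rests on the wording of the Inclusion criteria and the two arm sections. It assumes that silence in the intervention section means that no link is required there, not that one is prohibited. The practical gap may be confined to participants with prior severe hypoglycemia who are randomized to start with the intervention.

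**What to change.** - In the Inclusion criteria, replace the limit to the control arm with *during both arms of the study*.
- Add the companion-link sentence from the Control arm section to the intervention start visit, using the Dexcom G6 app already on the study phone.
- Set the link up at whichever arm comes first and check it at the second start visit. The existing start-up visit forms for the two arms can record its status.
- If Dexcom sharing cannot run alongside DailyDose, say so and name how the companion is alerted instead.

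No change is needed for the washout. The cost is a few minutes of set-up at a visit already planned to last 2 to 3 hours, plus a compatibility check before enrolment. If a substitute channel has to be found, that could cost more. Sample size, visit schedule and analysis stay as they are.

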### **Exclusion criteria**

- Individual of childbearing potential who is pregnant or intending to become pregnant or breast-feeding or is not using adequate contraceptive methods. Acceptable contraception includes birth control pill / patch / vaginal ring, Depo-Provera, Norplant, an IUD, the double barrier method (the woman uses a diaphragm and spermicide, and the man uses a condom), or abstinence
- Any active infection
- Known or suspected abuse of alcohol, narcotics, or illicit drugs (except marijuana use)
- Seizure disorder
- Use of non-insulin glucose lowering medications
- Use of steroids
- Stage-three or more advanced chronic kidney disease
- Cirrhosis
- Hypo- or hyper- thyroidism that is not medically optimized and on a stable regimen define as Thyroid-stimulating hormone (TSH) outside of the normal reference range based on screening labs
- Adrenal insufficiency
- Any life-threatening disease, including malignant neoplasms and medical history of malignant neoplasms within the past 5 years prior to screening (except basal and squamous cell skin cancer).
- Any clinically significant disease or disorder which in the opinion of the Investigator may jeopardize the participant's safety or compliance with the protocol
- Individual working night shifts

## **Subject recruiting**

Participants will be recruited from OHSU clinics, from flyers to be posted in approved places at OHSU or posted on the web to the clinical trials page for the OHSU Schnitzer Diabetes Clinic, to the Clinic's Facebook group, ads on Facebook, electronic newsletter or from the OHSU Subject Recruitment website. Handouts may also be made available to faculty at Tuality, Providence, Kaiser Permanent, and Legacy to pass along to patients/participants who show interest in the study. Records from OHSU Schnitzer Diabetes Clinic patients may be screened to find potential participants. Participants will also be recruited from a list of participants who participated in past OHSU studies who have agreed to be contacted regarding future studies (OHSU diabetes research registry and/or [www.clinicaltrials.gov](http://www.clinicaltrials.gov)). Participants will be contacted using the approved telephone screening script and email template. Non-English-speaking participants will not be recruited since this protocol would require the use of medical devices and mobile software that do not have non-English versions available.

This study will use Epic MyChart® to recruit potential participants. Researchers will send MRNs of potential participants that look eligible for the study to the EPIC research team. EPIC research will load the potential participants into the research recruitment in-basket. Researchers will then run the program and all MyChart® recruitment messages will send to potential participants asking them to participate. There is no risk of duplicate invitations as it is based on MyChart® accounts combined with Epic records and no duplication is possible.

Up to 40 participants may be screened in this study. Goal enrollment is 20 participants. Up to 3 participants will be replaced if needed, with a total enrollment of up to 23 participants.

## **Withdrawal Criteria**

A participant may withdraw at will at any time or at the discretion of the investigator. A participant must be withdrawn if the following applies:

- Protocol deviation having influence on efficacy or safety as judged by the Investigator
- Substantial and repeated non-compliance with trial procedures
- Pregnancy
- Intention of becoming pregnant

## **Study procedures**

### **Screening session**

Screening will take place within 12 weeks prior to the start of the first arm of the study. Screening visits will take place at OHSU's Biomedical Engineering Point of Care (BME POC) Laboratory, the Harold Schnitzer Diabetes Health Center, or virtually using WebEx. This visit will take approximately 1.5 hours.

The participant will be sent the consent form prior to the screening by email so that they can have time to read it fully at their leisure and prepare any questions they might have. Prior to any screening procedures, study staff will explain the study, give the participant ample time to ask

questions and consider participation, and ensure that the participant voices their understanding of the informed consent and study requirements. To minimize the possibility of coercion and to ensure that participant is signing the appropriate version of the consent, an informed consent checklist will be used by study staff. For virtual screening visits, participants will be consented over WebEx and study staff will witness them signing consent. Participants will sign two consent forms. After the participant has signed the consent, a copy of the consent/authorization form will be given or sent to OHSU staff by the participant. For virtual visits, participants will keep one copy of the signed consent form and ship one to OHSU overnight. The original will be kept for the source document.

Study personnel will review medical history and medications. A physical exam performed within the last year will be reviewed by investigator via chart review. Height and weight measures will be obtained both in clinic and using a home scale for in-person visits. For virtual visits, height and weight will be self-reported to staff; weight will be measured using a home scale or taken from clinic note within the past year. Blood pressure and heart rate will be obtained from chart review by study staff or from at-home monitoring unit (if participant is in possession of one).

Individuals of child-bearing potential will take a urine pregnancy test (UPT), which must be negative to participate. A venous blood sample will be taken for the following tests: hemoglobin A1C, complete blood count, complete metabolic set (including creatinine, liver set, and electrolytes) and thyroid-stimulating hormone (TSH). Blood draw labs and urine pregnancy testing will be completed within 1 week of screening at an OHSU outpatient phlebotomy lab. If a participant had any of these labs drawn with in the last 6 months and results are available for review within Epic or CareEverywhere for the study investigator to review, then those labs do not need to be drawn at this point.

A study investigator will assess inclusion/exclusion criteria and may review the participant's medical record for clarification as needed. The participant's glucose sensor data will be downloaded at the time of the screening visit or accessed online to confirm that the participant has experienced nocturnal hypoglycemia (i.e., two events) in the 30 days prior to the screening visit. A three-digit participant ID number will be assigned to the participant. Participants will complete hypoglycemia awareness, diabetes distress scale, hypoglycemia fear survey, and sleep quality questionnaires that will serve as a baseline to compare against results obtained at the end of the intervention period.

